9.1. Clinical Efficacy

All efficacy data will be summarized by treatment group (Nyxol or placebo) and visit (Day 1, Day 8, and Day 15).

9.1.1. Primary Efficacy Analysis

[REDACTED]

[REDACTED]

[REDACTED]

By including [REDACTED] primary efficacy analysis model, the model efficiency as well as a change in the treatment effect will be increased. Including this factor in the model will also make the results more generalizable to other studies in which the sample characteristics may differ from the current study [2]. Additionally, a sensitivity analysis will be applied to the primary efficacy endpoint for the mITT and PP populations,

which uses a logistic regression model with only treatment as a [REDACTED] [REDACTED].

For the analysis of the PP Population, subjects who did not dose the night before, or the morning of, their Day 15 visit will be excluded from the Day 15 visit summary.

In addition, the primary efficacy endpoint [REDACTED] using the same model indicated above [REDACTED]. For these subgroup analyses, observed case data only will be used; that is, missing values will not be imputed.

9.1.2. Secondary and Exploratory Efficacy Analysis

Secondary and exploratory efficacy endpoints are indicated in [Section 4.2.2](#). Secondary and exploratory efficacy endpoints will be analyzed by study eye, non-study eye, the best of either eye, and binocular, unless otherwise indicated.

Visual acuity assessments (mLCVA, pLCVA, mHCVA, and DCNVA) will be summarized using letters. For mLCVA, pLCVA, and mHCVA, the assessments will also be summarized using logMAR units. Only letters will be recorded in the CRF. Letters will be converted to logMAR using the following formula: $\text{logMAR} = 0.02 * (\text{S} - \# \text{ Letters})$, where $\text{S} = 55$. The values of S are the number of letters read equivalent to a Snellen Acuity of 20/20. For example, for mLCVA, if the # letters = 55, then $\text{logMAR} = 0.02 * (55 - 55) = 0.00$; if # letters > 55, then logMAR is negative.

Each of the continuous secondary efficacy endpoints will be analyzed using analysis of covariance (ANCOVA), with change from baseline as the dependent variable, treatment, and [REDACTED] and the respective baseline value included as the covariate.

Each ANCOVA will be performed using the mITT and PP populations. The output from each ANCOVA will include the LSM and SE for both treatment groups, along with the placebo-corrected LSM, its 95% CI and associated p-value.

For each of the secondary endpoints related to percent of subjects achieving certain criteria, the analysis will be performed using a logistic regression model with treatment [REDACTED] [REDACTED]s, and the respective baseline as a covariate. For each analysis, the percentage of subjects in each treatment group meeting the criteria, the OR with 95% CI and p-value will be provided.

In addition, each secondary efficacy endpoint will be analyzed by [REDACTED] the same model indicated above but without irides as a factor.

For Day 8 and Day 15, the time since last dose of study treatment will be calculated as follows: date/time of visit minus date/time of the most recent dose of study medication in the subject diary. [REDACTED]

[REDACTED] For each subject, the category could be different for Day 8 and Day 15. Summaries of improvement in mLCVA, and change and percent change in pupil diameter, will be presented based on these categorizations.

Questions from the subject questionnaire, including those questions for which it is not appropriate to be analyzed using the methods above, will be summarized categorically for each treatment group and visit, as well as by [REDACTED]

10. SAFETY ANALYSES

All safety analyses will be conducted using the SP. All safety analyses will be completed using the actual treatment a subject received. Observed case data will be used; no imputation will be performed for missing safety data except for the limited situations described in [Section 7.3.2](#).

All safety data will be presented in by-subject listings. Unscheduled assessments will not be summarized but will be included in the listings.

10.1. Adverse Events

AEs will be coded using MedDRA, Version 23.1.

Treatment-emergent adverse events (TEAEs) are defined as any AE that begins or worsens after initiation of the investigational product and through the subject's last study visit (study completion/follow-up phone call, or early termination).

If the onset of an AE is on or after the date of first dose of study medication or is increasing in severity after first dose of study medication, then the AE will be considered treatment emergent.

Only TEAEs will be summarized; all AEs (TEAE, non-TEAE) will be included in a by-subject listing.

The number and percent of subjects with any TEAEs will be summarized by SOC and PT by treatment group and overall. At each level of tabulation (e.g., at the PT level), subjects will be counted only once if they had more than one such event reported during the AE collection period.

Note that in MedDRA, ocular events are coded to the SOC of "Eye Disorders". Thus, using SOC in the summaries will provide a separation of ocular and non-ocular adverse events.

The following summary tables will be presented for TEAE data:

- Overall summary of TEAEs
- Summary table of TEAEs by SOC and PT
- Summary table of TEAEs by SOC, PT, and by greatest relationship level to study drug (not related, unlikely related, possibly related, probably related, definitely related, or unknown)
- Summary table of TEAEs by SOC, PT, and maximum severity (mild, moderate, severe)
- Summary table of serious TEAEs by SOC and PT
- Summary table of TEAEs leading to withdrawal from the study by SOC and PT
- Summary table of TEAEs leading to study medication discontinuation by SOC and

PT

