8.3 Adverse Events and Serious Adverse Events

All AEs and SAEs that occur following consent and until the final study visit should be collected and recorded on the AE or SAE eCRF page. Only treatment-emergent adverse events/adverse reactions (TEAEs) will be summarized ([Section 9.3.5](#)).

All AEs/adverse reactions occurring during the study (i.e., once the subject has signed the informed consent/assent) **must** be documented, regardless of the assumption of causal relationship, on the respective eCRF. All TEAEs/adverse reactions must be documented from the time the subject receives the study medication until the subject's participation in the study has been completed. If a subject has ongoing AEs/adverse reactions at the time of study completion or discontinuation from the study, the ongoing AEs/adverse reactions **must** be followed-up and provided appropriate medical care until the signs and symptoms

have remitted or stabilized or until medical assessments have returned to acceptable or pre-study limits.

Documentation of AEs/adverse reactions includes start date and end date, severity, relationship to study medications, action(s) taken, seriousness, and outcome.

8.3.1 *Adverse Event Definitions*

The following definitions of terms apply to this section:

Adverse event. An AE is any untoward medical occurrence associated with the use of a study medication in humans, whether or not considered drug related. An AE can therefore be any unfavorable and unintended sign (including abnormal laboratory findings), symptom, or disease temporarily associated with the use of the study medication, whether or not related to the study medication. Study medication includes the investigational drug under evaluation and the comparator product or vehicle placebo that is given or administered during any phase of the study.

Medical conditions/diseases present before starting the investigational treatment are only considered AEs if they worsen after starting the investigational treatment. Abnormal test results constitute AEs only if they induce clinical signs or symptoms, are considered clinically significant, or require therapy.

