- Redness related to instillation that is transient (i.e., is no longer present 2 hours after instillation) = “conjunctival erythema upon instillation”
- Redness that is NOT transient (i.e., is present \geq 2 hours after instillation) = “conjunctival hyperemia”

Expedited reporting of Serious and Unexpected Adverse Events: All SAEs (related and unrelated) will be recorded following subject signature of the informed consent/assent and until the Follow-up Visit. Any SAEs “suspected” to be related to the study medication and discovered by the Investigator at any time **after** the study should be reported.

Any SAE that occurs must be reported to the CRO within 24 hours of its occurrence or within 24 hours of learning of its occurrence. Recurrent episodes, complications, or

progression of the initial SAE must be reported to the CRO as follow-up to the original episode within 24 hours of the Investigator receiving the information. Information about all SAEs will be collected and recorded on the SAE form. All pertinent medical records and information collected during the treatment and follow-up of the subject should be maintained at the site with a copy emailed to [REDACTED]. The Investigator must assess the SAE relationship and complete the SAE form. The CRO may request additional information. Follow-up information (e.g., discharge summary) will be retained in the subject's chart and a copy will be emailed to [REDACTED]. In addition, all SAEs should be recorded on the AE eCRF page with the serious question marked "Yes".

It is the Investigator's responsibility to notify the approving IRB of any SAEs on a timely basis as instructed by Ocuphire following Ocuphire's determination of causality. All subjects who experience an SAE should be followed clinically and undergo the appropriate diagnostic evaluations until stabilization or resolution of the event. Ocuphire will report all SAEs to the FDA on the appropriate schedule depending if the event is drug related or not drug related, expected, unexpected (based on the available information in the IB).

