Safety will be assessed using the SP with subjects included in the treatment group they actually received, regardless of their randomized treatment. Observed case data will be used; no imputation will be performed for missing safety data. A statistical analysis of conjunctival hyperemia will be conducted as described below; otherwise, no statistical analysis of safety data will be performed.

For HR and BP, baseline value is defined as the screening value. HR and BP values and change from baseline in the values will be summarized by treatment group and timepoint (Day 1, Day 8, and Day 15).

Observed values and change from baseline (Day 1) in conjunctival hyperemia at each visit (Day 8 and Day 15), will be summarized for the study eye, the non-study eye, and the best of either eye. Treatments will be compared using the same ANCOVA model proposed for the continuous secondary efficacy endpoints.

For IOP, baseline is defined as the baseline value of Visit 1 (Day 1). Observed values and change from baseline in IOP at Day 8 and Day 15 will be summarized for the study eye, the non-study eye, and the best of either eye.

Subject questionnaire values will be summarized by treatment group and timepoint (Day 1, Day 8, and Day 15).

Verbatim descriptions of AEs will be coded using MedDRA. Only TEAEs (those that occur after the first dose of study medication *or increasing in severity after initiation of study medication*) will be summarized. TEAEs and SAEs will be summarized by treatment group, by system organ class (SOC), severity, and relationship to study medication. Deaths, withdrawal from study medication due to AEs, and withdrawal from the study due to AEs will each be summarized by treatment group. Note that in MedDRA, ocular events are coded to the SOC of “special senses”. Thus, using SOC in the summaries will provide a separation of ocular and non-ocular AEs.

All safety data will be provided in by-subject listings.

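### Ocular and non-ocular adverse events are to be separated by system organ class alone; the two documents name different classes, and neither has a rule for eye events coded elsewhere

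*SAP*

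**What the plan says.** Protocol 9.3.6 has adverse events coded from the investigator's text ("Verbatim descriptions of AEs will be coded using MedDRA"). It then states that "ocular events are coded to the SOC of “special senses" and concludes: "Thus, using SOC in the summaries will provide a separation of ocular and non-ocular AEs".

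SAP 10.1 uses the same dictionary, fixed at version 23.1, but states that "ocular events are coded to the SOC of 'Eye Disorders". It draws the same conclusion, that "using SOC in the summaries will provide a separation of ocular and non-ocular adverse events". Its list of planned summaries has an overall table and several tables by SOC and preferred term. It has none by ocular status. Subjects are counted once at each level of tabulation.

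SAP 3.3, which lists the changes from the protocol, does not mention the change of class name. It says that the analyses are otherwise consistent with the protocol.

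**The concern.** This is an eye drop, and Protocol 4.1 makes adverse events one of two primary safety measures, beside conjunctival hyperemia. A reader will want to know how many subjects in each arm had any ocular event. The plan's only readable answer is to look at one class, and the documents disagree on its name.

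The name is the smaller matter. The larger one is that the rule reads site from a dictionary class. An eye event whose coded term sits in another class would be read as non-ocular, and nothing in the plan would bring it back. At stake is the subject-level split between ocular and non-ocular events. The record of any event, the efficacy tests and the primary conclusion are not affected.

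**Working it through.** No plan figure exists to reproduce. The check compares the texts and adds a short counting argument.

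**1. Class name.** Protocol 9.3.6 gives *special senses* and SAP 10.1 gives *Eye Disorders*. Both attribute the class to MedDRA, so at most one can be the name in the version used.

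**2. What sets the class.** Protocol 9.3.6 codes the verbatim description. SAP 7.3.5 maps events to preferred term and body system. Affected eye is not an input at either step.

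**3. When the rule is right.** It needs every eye event to map to the one named class. Neither document shows this or gives a fallback.

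**4. Where it could fail here.**
- Protocol 8.3.1 prescribes a verbatim term for "Redness related to instillation that is transient (i.e., is no longer present 2 hours after instillation"). The term names the conjunctiva and also the act of instillation, so the plan's text does not settle its class.
- Protocol 8.3.1 lets an abnormal test result count as an adverse event if it causes signs or symptoms, is clinically significant or needs therapy. IOP is a measured safety parameter (Protocol 8.1).

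That either would code outside the named class is an assumption, since the dictionary hierarchy is not in the documents.

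**5. Data to repair it.** Protocol 8.3 says: "Documentation of AEs/adverse reactions includes start date and end date, severity, relationship to study medications, action(s) taken, seriousness, and outcome". Affected eye is not among these items. The list is introduced by a non-exhaustive verb, and the case report form is not in the public documents, so an eye field may exist.

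**6. Can the ocular total be rebuilt from the SOC tables?** In one arm, let
- *n* = subjects in the arm,
- *a* = subjects with at least one event in the named class,
- *b* = subjects with at least one eye event in any other class,
- *T* = subjects with any eye event.

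Take all events in the named class to be eye events. Then max(*a*, *b*) ≤ *T* ≤ min(*a* + *b*, *n*). The SOC row shows *a*. The shortfall *T* − *a* is the number of subjects whose eye events all lie outside the named class. It runs from max(0, *b* − *a*) to min(*b*, *n* − *a*). The tables do not show how many subjects are in both groups, so *T* cannot be obtained by adding rows. It needs a subject-level flag.

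**7. Contrast inside the SAP.** SAP 8.4 summarizes ocular and non-ocular medical history separately, although that history is coded in the same dictionary. The adverse-event section has no matching table.

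**The case against.** The case against giving this weight is substantial, and most of it stands.

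- **The dictionary is absent.** The documents cannot show that any particular eye term falls outside the named class. Only the possibility follows from the text. The instillation term does name the conjunctiva, and redness still present two hours or more after instillation is recorded as conjunctival hyperemia.
- **The main eye signals are analyzed without SOC.** Hyperemia grades (SAP 10.3) and IOP (SAP 10.5) are summarized by eye and compared by ANCOVA. Biomicroscopy and ophthalmoscopy are summarized by arm (SAP 10.6). One limit applies: hyperemia is graded at clinic visits while doses are taken in the evening, so redness gone within two hours of a dose would usually appear only as an adverse event.
- **Nothing is hidden.** Every treatment-emergent event appears by preferred term and arm, and all events are listed.
- **No pooled ocular rate is listed in SAP 10.1.** The planned-table list in SAP 12.1 is not shown, so a pooled table can be neither assumed nor excluded.
- **The SAP governs the tables,** so the protocol's class name changes no output.

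Three stronger readings are tempting, and the documents do not support them.

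- *Ocular incidence on Nyxol will be understated relative to placebo.* Placebo is also instilled as drops, and no instillation event rates by arm are given.
- *The shortfall has a known size.* Assume 30% of subjects have an eye event and a share *s* of them have one coded outside the named class. The rate shown then lies between 30% × (1 − *s*) and 30%: 22.5% to 30% for *s* = 0.25, and 15% to 30% for *s* = 0.50. Both inputs are invented. The lower ends require that none of the affected subjects has another event in the named class.
- *Eye infections are an expected source of misplaced terms.* Ocular infection appears in the protocol only as an exclusion criterion.

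What remains is that the stated rule claims a separation it cannot guarantee, and that the SOC tables alone cannot supply the subject-level ocular count.

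**Conclusion.** The point holds as a minor one. Three parts are direct text: the class names conflict, both documents rely on SOC alone, and class is set by the coded term. That an eye event could be counted as non-ocular is an inference from the lack of any safeguard. It becomes real only if at least one eye term codes outside the named class. It lowers the ocular subject count only where a subject has no other event in that class.

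The size is not computable from the documents. It may be zero, and its direction by arm is unknown. The change is worth making because adverse events are a primary safety measure of a topical eye product and a better rule costs little.

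**What to change.** 1. Check the class name against MedDRA 23.1 and use one name in both documents. If the protocol is not to be amended for this alone, record the correction in SAP 3.3.
2. Replace the SOC sentence in SAP 10.1 with a rule such as:

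> Before unmasking, a masked reviewer will classify each TEAE as ocular or non-ocular from its preferred term and verbatim text, and from the affected eye where the eCRF records it. The number and percentage of subjects with any ocular and any non-ocular TEAE will be tabulated by treatment group from this flag, whatever the SOC.

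3. Keep the SOC and preferred-term tables as planned, and show the flag in the adverse-event listing.

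The cost is a short masked term review and one extra table, with no new data collection. SAP 8.2 already provides a blinded sponsor review of protocol deviations before database lock, and the term review can run beside it.

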10.2. Deaths, Serious Adverse Events and Other Significant Adverse Events

10.2.1. Deaths

The AE listing will include all AEs, including deaths, regardless of causality; one of the columns in the listing will specify whether the AE was fatal.

10.2.2. Serious Adverse Events

The AE listing will include all AEs, including SAEs; one of the columns in the listing will specify whether the AE was an SAE.

10.2.3. Adverse Events Leading to Withdrawal from the Study

The AE listing will include all AEs, including AEs leading to withdrawal from the study; one of the columns in the listing will specify whether the AE led to withdrawal from the study.

10.2.4. Adverse Events Leading to Discontinuation of Study Medication

The AE listing will include all AEs, including AEs leading to discontinuation of study medication; one of the columns in the listing will specify whether the AE led to discontinuation of study medication.

10.3. Conjunctival Hyperemia

Results from the conjunctival hyperemia assessment, measured with a CCLRU card 4-point scale, will be summarized descriptively using counts and percentages for each treatment group at each visit (Day 1, Day 8, and Day 15) for the observed value and change from baseline (Day 1). Separate summaries will be created for the study eye, the non-study eye, and the best of either eye.

Additionally, conjunctival hyperemia will be summarized as a continuous variable. Treatments will be compared using the same ANCOVA model proposed for the continuous secondary efficacy endpoints.

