In this study, Nyxol had statistically significant PD reductions under photopic and mesopic conditions that were sustained for 36 hours post-dosing. A statistically significant number of patients with Nyxol compared to placebo demonstrated ≥ 1 line of improvement in DCNVA, with a trend for 2- and 3-line improvements at all time points. There was no statistical difference in conjunctival hyperemia compared to placebo. In summary, daily evening dosing of Nyxol was found to be well tolerated with no daytime conjunctival redness and demonstrated improvement in DCNVA with sustained PD reduction in a glaucomatous and presbyopic population. Smaller pupil size can have beneficial effects in improving symptoms of patients with DLD, which is relevant to the LYNX-1 trial.

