4 STUDY DESIGN

4.1 Primary and Secondary Endpoints

Efficacy:

The primary efficacy endpoint is the percent of subjects with ≥ 15 ETDRS letters (≥ 3 lines) of improvement in the study eye compared to baseline in monocular mLCVA at Day 8.

The eye with the greatest mLCVA improvement [REDACTED]

[REDACTED]
[REDACTED]
[REDACTED]
[REDACTED]
[REDACTED]

[REDACTED] The study eye and non-study eye, as well as binocular, will both be evaluated at all appropriate assessments.

All treatments will be administered OU.

Secondary efficacy endpoints (for the study eye, the non-study eye, the best of either eye, and binocular) will include:

- [REDACTED]
[REDACTED]
[REDACTED]
- [REDACTED]
[REDACTED]
- [REDACTED]
[REDACTED]
[REDACTED]
[REDACTED]
- [REDACTED]
[REDACTED]
- [REDACTED]
[REDACTED]
[REDACTED]
- [REDACTED]
[REDACTED]

Exploratory efficacy endpoints (for the study eye, the non-study eye, the best of either eye, and binocular) will be collected and analyzed for the sites that have an OPD Scanner and will include but are not limited to:

- [REDACTED]
- [REDACTED]
- [REDACTED]

In addition, data captured by OPD Scan III per subject per applicable visit will be generated. These data include graphs, heatmaps, vision simulations, numerical data, point spread function, Zernike graphs, VA-ETDRS simulations, angle kappa, etc. Exploratory analyses may be completed using these data.

Measurements (Appendix 2):

Safety:

The primary safety measures are conjunctival hyperemia and AEs.

Analysis for conjunctival hyperemia includes change from baseline (Day 1) in the conjunctival hyperemia grading scale (CCLRU images) at each visit (Day 8 and Day 15), for study eye and non-study eye. Any increase of 2 units in conjunctival hyperemia between consecutive visits is considered an AE.

Other safety measures include IOP, biomicroscopy, ophthalmoscopy, dry eye measurements, and systemic safety as measured by HR and BP. Urine pregnancy tests for females of childbearing potential will be conducted.

Subject questionnaire values will be summarized by treatment group and visits (Day 1, Day 8, and Day 15).

Measurements:

- Conjunctival hyperemia will be assessed visually with a grading scale (0-3) using images from the CCLRU.
- IOP will be measured with the Tono-Pen.
- BP and HR will be measured manually or with available digital devices.
- Subject questionnaire will be a brief symptom survey ([Appendix 3](#)).

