5.4. Analysis Variables

Variables to be summarized include demographics and baseline characteristics, medical (non-ocular) and ocular history, concomitant medications, and study drug accountability.

Efficacy variables include:

- Mesopic low-contrast BCDVA (mLCVA)
- Photopic low-contrast BCDVA (pLCVA)
- Mesopic high-contrast BCDVA (mHCVA)
- Mesopic high-contrast DCNVA
- Photopic pupil diameter

- Mesopic pupil diameter
- Total RMS error (score) and higher-order RMS (spherical, coma, trefoil) error
- Subject questionnaire

Safety variables include:

- Conjunctival hyperemia (eye redness) measured with a CCLRU card 4-point scale:
 - None (0) = Normal Appears white with a small number of conjunctival blood vessel easily observed.
 - Mild (+1) = Prominent, pinkish-red color of both the bulbar and palpebral conjunctiva.
 - Moderate (+2) = Bright, scarlet red color of the bulbar and palpebral conjunctiva.
 - Severe (+3) = Beefy red with petechiae, dark red bulbar and palpebral conjunctiva with evidence of subconjunctival hemorrhage.
- AEs
- Vital signs (HR and BP)
- IOP
- Biomicroscopy
- Ophthalmoscopy
- Urine pregnancy tests for females of childbearing potential

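### The best-of-either-eye summary carried from efficacy to conjunctival hyperemia (and, with less consequence, IOP) naturally shows the less affected eye and is undefined for change; a worst-eye summary suits safety better (minor)

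*SAP*

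**What the plan says.** Protocol 4.1 sets the status of the measure: "The primary safety measures are conjunctival hyperemia and AEs". It also states "All treatments will be administered OU", so either eye can show harm. Its own description of the hyperemia analysis (change from Day 1 at Day 8 and Day 15) names the study eye and the non-study eye only.

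Protocol 9.3.6 goes further. Hyperemia and IOP "will be summarized for the study eye, the non-study eye, and the best of either eye". SAP 10.3 (hyperemia) and SAP 10.5 (IOP) follow it: "Separate summaries will be created for the study eye, the non-study eye, and the best of either eye". Both cover observed values and change from baseline.

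The phrase is also the efficacy convention. SAP 9.1.2 reads: "Secondary and exploratory efficacy endpoints will be analyzed by study eye, non-study eye, the best of either eye, and binocular". The direction of the redness scale is given in SAP 5.4, where 0 is normal and the top grade is "Severe (+3) = Beefy red with petechiae, dark red bulbar and palpebral conjunctiva with evidence of subconjunctival hemorrhage".

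Two other provisions bear on the point. Protocol 4.1 and 8.3.1 make any 2-unit rise in hyperemia between consecutive visits an adverse event, without naming an eye. In the TEAE tables (SAP 10.1), "subjects will be counted only once if they had more than one such event reported during the AE collection period".

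**The concern.** For visual acuity, the better of two eyes is a natural summary of benefit. For redness, the same convention points the other way. If *best* means the lower grade, a subject counts as affected only when both eyes are affected. The one stated summary that combines the two eyes' grades would then be the most favorable of the three, for a primary safety measure and a drug given to both eyes.

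The second problem is definition. No visible text says whether *best* is chosen on the observed value or on the change, or whether the same eye is kept across visits. Two programmers could produce different change tables from the same wording.

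At stake is how clearly local tolerability is reported. Efficacy is not affected.

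**Working it through.** The plan gives no figure to reproduce. Every rate, SD and correlation below is an assumption used to show direction and range.

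**1. Best eye versus worst eye.** Let *p* be the proportion of eyes affected at a visit and φ the between-eye correlation.

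- Best eye affected = both eyes affected = p² + φ·p·(1−p)
- Worst eye affected = either eye affected = 2p − best

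For p = 0.20 and φ = 0.8: best = 0.04 + 0.8 × 0.16 = 0.168; worst = 0.40 − 0.168 = 0.232.

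| p per eye | φ | best eye | worst eye |
|---|---|---|---|
| 20% | 0.5 | 12.0% | 28.0% |
| 20% | 0.8 | 16.8% | 23.2% |
| 20% | 0.95 | 19.2% | 20.8% |
| 20% | 1 | 20.0% | 20.0% |
| 5% | 0.5 | 2.6% | 7.4% |
| 5% | 0.8 | 4.1% | 6.0% |
| 5% | 0.95 | 4.8% | 5.2% |

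The best-eye rate never exceeds the single-eye rate. It equals the worst-eye rate only if the eyes always agree.

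**2. What a reader can recover.** At one visit, with both eyes graded, either-eye rate = study eye + non-study eye − best eye. For change, this works only if *best* means the smaller change. Across two visits the summaries give only bounds, from the larger visit rate to the sum of the two. With 23.2% at each visit, that is 23.2% to 46.4%.

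**3. The undefined change.** Suppose eye 1 goes from 0 to 2 and eye 2 stays at 1.

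- Smaller of the two changes: min(2, 0) = 0
- Best grade at visit minus best grade at baseline: min(2, 1) − min(0, 1) = 1 − 0 = +1
- Worst-eye change: max(2, 0) = +2

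Over all 4⁴ = 256 combinations of baseline and visit grades in two eyes, the first two readings differ in 142. If both eyes start at the same grade *b*, then min(v₁−b, v₂−b) = min(v₁, v₂) − b, so the readings agree in all 4 × 16 = 64 such patterns. All 142 disagreements therefore need unequal baseline grades. This is a count of patterns, not a probability.

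**4. What the adverse-event rule catches.** Read the rule as covering rises of 2 or more units in either eye. Day 1 to Day 8 is a consecutive pair, so every such rise at Day 8 is already an adverse event. A rise of 2 or more from Day 1 escapes only if neither step reaches 2, which means two one-grade steps: 0-1-2 or 1-2-3 over Days 1, 8 and 15. One-grade rises never trigger the rule.

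**5. IOP.** The documents state no direction; higher is taken as worse. For two exchangeable normal eyes, mean of the higher eye − mean of the lower eye = 2·SD·√((1−ρ)/π).

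- SD 2, ρ 0.95: 0.50 mmHg
- SD 3, ρ 0.8: 1.51 mmHg
- SD 4, ρ 0.7: 2.47 mmHg

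An equal shift in both eyes leaves the difference between arms unchanged. For IOP the choice therefore affects the reported level and rises in one eye only.

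**The case against.** The strongest reply is that little is hidden. The study eye and non-study eye are each summarized without selection, and Protocol 4.1 names only those two for hyperemia, so the best-eye summary is an addition. All safety data are listed (SAP 10). Biomicroscopy, which covers the conjunctiva (Protocol 8.1), is summarized at Day 1 and Day 15 (SAP 10.6). The adverse-event rule captures 2-unit rises per subject. Redness at clinic visits may also be rare: Protocol 2.2 reports of the earlier 14-day study that "daily evening dosing of Nyxol was found to be well tolerated with no daytime conjunctival redness". Both eyes receive the same drop, so they may largely agree.

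Most of this stands, and it makes the point minor. It does not justify a third summary that selects the less affected eye, nor does it supply the missing definition. The adverse-event rule has gaps (step 4), and the visible text has no matching rule for IOP.

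A reader might infer four stronger things that the documents do not support:

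- *That the plan reports only the favorable eye.* Three sets of summaries are stated, and two select nothing.
- *That the treatment comparison is biased.* SAP 10.3 does not say that the ANCOVA uses the best-eye value.
- *That 2-grade rises in either eye go uncounted.* Most are adverse events by rule, although the preferred-term row may also contain milder reported redness and so is not a clean count.
- *That 142 of 256 measures how often the ambiguity matters.* It gives implausible unequal baselines the same weight as common ones.

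**Conclusion.** The point holds as a minor one. SAP 10.3 and 10.5 and Protocol 9.3.6 apply an efficacy convention to measures where the more affected eye is the one of interest, and the visible text leaves it undefined for change.

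On the assumed values, the gap between best-eye and worst-eye redness rates runs from 16 percentage points (20% per eye, correlation 0.5) to under 1 point (5% per eye, correlation 0.95), and to zero if the eyes always agree. The IOP part is slight.

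The conclusion rests on two things. First, *best* is taken to mean the lower grade or pressure, which is the natural reading but not a stated rule. Second, the contents of the planned-table list (SAP 12.1) and some endpoint text are not visible, so a definition or a worst-eye table there cannot be excluded. If one exists, a cross-reference in 10.3 and 10.5 would settle the definition.

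**What to change.** In SAP 10.3 and 10.5, replace or supplement the best-eye summary with: *the worst of either eye (observed value: the higher grade or IOP of the two eyes at that visit; change: the larger increase from baseline of the two eyes)*. If the best-eye summary is kept, define it for both observed value and change.

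Align Protocol 4.1 and 9.3.6, which differ from each other on this for hyperemia, or record the difference in SAP 3.3.

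Optionally, add to SAP 10.3 the number and percentage of subjects per arm with any rise from Day 1 in either eye at Day 8 or Day 15. This is the figure the stated summaries cannot give. A count limited to rises of 2 or more grades would largely repeat the adverse-event rule.

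If these tables are added after unmasking, label them post hoc.

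The cost is one or two derived variables from data already collected, with no new assessments. The downside is one more table per measure and a possibly higher reported redness rate.
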